4.2. Scientific Rationale for Study Design

This study was designed to be consistent with the US Food and Drug Administration (FDA) Guidance for Industry on Providing Clinical Evidence of Effectiveness for Human Drug and Biological Products, the International Conference on Harmonisation (ICH) E1A and E8 Guidance, and with the ethical principles in these guidances that originate in the Declaration of Helsinki.

The target patient population is participants with moderate to severe ET, which was selected to reflect the patient population within clinical practice for whom a therapeutic intervention for ET

Protocol JZP385-201-04 Amendment 04

would be considered. Patients with mild ET are typically not treated with medication, as the tremor is not usually associated with significant functional disability (Gironell and Kulisevsky, 2009; Louis, 2010; Rajput and Rajput, 2014). Essential tremor severity level in this study will be defined by eligibility criteria on patient-rated (TETRAS-ADL) and clinician-rated (CGI-S) measures of disability. The inclusion of a placebo control group in this study is necessary to determine the efficacy and safety of JZP385.

The 12-week duration (which includes up to 3 weeks of titration and a minimum of 9 weeks at the assigned fixed dose) is considered as adequate duration to detect efficacy and evaluate safety in this phase 2b study. Based on results from the T-CALM study, efficacy signals were observed at both time points tested: the end of Week 2 (at 16 mg/day [8 mg BID]) and the end of Week 4 (at 20 mg/day [10 mg BID]). Adverse events were primarily reported during the first week of treatment and the majority of the commonly reported AEs resolved within a week of onset. A longer treatment duration of 12 weeks with clinic visits to assess safety at multiple time points (Weeks 1, 4, 8, and 12), combined with weekly phone calls for AE reporting, will allow for an adequate assessment of safety and durability of the treatment effect.

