4.3. Justification for Dose

The doses of JZP385 being evaluated in the study are 10, 20, and 30 mg/day administered in the morning. In the T-CALM study conducted in patients with ET, daily doses of 16 and 20 mg/day JZP385 (administered as the IR formulation at doses of 8 and 10 mg BID, respectively), improved symptoms of tremor across several clinically meaningful endpoints, including the TETRAS-ADL subscale, and were safe and well tolerated. Preliminary PK data and subsequent

PK simulations from the relative bioavailability study (Study CX-8998-CLN2-005) indicate that the same daily doses of the IR and ER formulations produce similar exposures (ie, steady state daily AUC). Therefore, this study will further evaluate the safety and efficacy of 20 mg/day JZP385, in addition to a higher dose of 30 mg/day and a lower dose of 10 mg/day administered orally, once daily in the morning. Preliminary safety and tolerability data from study JZP385-101, which enrolled 100 healthy older volunteers with a mean age of 44.1 years (median = 42.9 years; range 23 to 76 years) indicate that titrated doses of up to 36 mg were generally safe and well tolerated.

The titration schedule in this protocol is based on the PK of JZP385, as well as the titration experience in previous clinical studies conducted to date. Steady state levels of JZP385 are reached in 5 days. In the T-CALM study in patients with ET, participants received the IR formulation of JZP385 for 1 week each at doses of 8 and 16 mg/day before the final dose of 20 mg/day (doses were administered as 4, 8 and 10 mg BID, respectively). Preliminary safety and tolerability data from study JZP385-101 also indicate that the starting dose of 8 mg/day of the ER formulation of JZP385, with dose escalation at weekly intervals, was generally safe and well tolerated in healthy volunteers. Although these data indicate the 8 mg/day dose is tolerated as a starting dose, all participants in this study will initially receive 5 mg/day for the first week of the treatment period to evaluate whether starting at a lower dose may further improve tolerability.

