9.4.5. Safety Analysis

All safety analyses will be performed on the Safety Population. Safety analyses will be descriptive; no formal statistical testing will be performed.

Adverse Event Analyses:

Adverse events will be mapped to system organ classes and preferred terms using the Medical Dictionary for Regulatory Activities (MedDRA). The participant incidence of AEs, AEs related to study intervention, SAEs, AEs leading to discontinuation, and fatal AEs will be summarized. This overall summary will also provide AEs by maximum severity.

The participant incidence of AEs, AEs related to study intervention, AEs, and AEs leading to discontinuation will also be presented by SOC and preferred term. Preferred term summaries may also be provided.

The participant incidence of an AE will be summarized; if a participant has multiple events with the same PT occurring in different periods, the event will be reported for each of those periods. Multiple increases in severity will only be counted as one AE.

Vital Signs:

For each vital sign parameter, summary statistics will be provided for observed and change from baseline values by scheduled visit.

Protocol JZP385-201-04 Amendment 04

Physical Examinations

Observed and change from baseline values for weight will be summarized descriptively by scheduled visit.

12-lead ECG

Observed and change from baseline values for ECG intervals will be summarized descriptively. QT abnormalities will be assessed; the number and percent of participants with values or change from baseline values exceeding certain thresholds will be tabulated.

Laboratory Evaluations

Observed and change from baseline laboratory evaluations will be summarized descriptively.

C-SSRS

Columbia Suicide Severity Rating Scale parameters will be summarized by scheduled visit.

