4.1.3. Secondary Objectives

The secondary objectives of the study are:

- To evaluate the efficacy of JZP385 to improve overall ET when administered once daily for up to 12 weeks at fixed doses of 10, 20, and 30 mg/day.
- To evaluate the safety and tolerability of JZP385 administered once daily for up to 12 weeks at fixed doses of 10, 20, and 30 mg/day in the treatment of adult participants with ET.

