5. STUDY DESIGN

5.1. Summary of Study Design

This is a 12-week, double-blind, placebo-controlled, randomized, parallel-group, multicenter study of the safety and efficacy of JZP385 in the treatment of adult participants with moderate to severe ET.

[figure not shown]
The total duration of the study for each participant will be approximately 19 weeks. During the Screening Period, which will occur over a period of up to 35 days (an additional 28 days are permitted for participants who require washout of primidone), all participants will be evaluated for eligibility and will washout any prohibited medications. Participants eligible for the study will be randomized in a 1:1:1:1 ratio to receive once daily doses of 10, 20, or 30 mg JZP385 or placebo during a 12-week Double-blind Treatment Period. Randomization will be stratified by the TETRAS composite outcome score (≤ 17 or > 17) and the use of concomitant antitremor medication (Yes or No), as assessed at the Baseline Visit. JZP385 will be administered orally (PO) once daily in the morning on an empty stomach for 12 weeks. Dosing will be titrated as follows:

- Participants randomized to the 10 mg/day dose will initially receive 5 mg/day from Day 1 through Day 7, and 10 mg/day starting on Day 8.
- Participants randomized to the 20 mg/day dose will initially receive 5 mg/day from Day 1 through Day 7, 10 mg/day from Day 8 through Day 14, and 20 mg/day starting on Day 15.
- Participants randomized to the 30 mg/day dose will initially receive 5 mg/day from Day 1 through Day 7, 10 mg/day from Day 8 through Day 14, 20 mg/day from Day 15 through Day 21, and 30 mg/day starting on Day 22.

Once participants reach their assigned fixed dose, they will continue on that dose for the remainder of the planned 12-week treatment period. No dose adjustments will be allowed. Participants who cannot tolerate their assigned fixed dose of JZP385 will be withdrawn from the study.

The schema of study is shown in Figure 1.

Figure 1 Study Schema

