10.2. Adverse Events

Adverse events (AEs) occurring from the first dose until the final study visit will be reported. If the Investigator becomes aware of a SAE within 14 days after the last dose of study intervention, the event must also be reported. In addition, any SAE assessed as related to study intervention or procedure by the Investigator must be reported regardless of time after study termination.

AEs will be coded to system organ class (SOC) and preferred term using the Medical Dictionary for Regulatory Activities (MedDRA), Version 27.0. The investigator will assess the relationship of each AE to study intervention. AE with a missing relationship to study intervention will be reported as related in the summaries. Severity, as determined by the Investigator, will be classed as mild, moderate, severe, life-threatening or fatal. AE with missing severity will be reported as missing in the summaries.

Note that participants who acquire COVID-19 or report AEs due to the COVID-19 public health emergency (e.g., anxiety) while on study will be coded accordingly and included in the adverse event summaries.

A treatment-emergent adverse event (TEAE) is defined as any event with onset date on or after the first dose of study intervention, including adverse events that occur until 14 days after the last dose date. For the purpose of calculating treatment emergence, incomplete onset dates will be imputed as detailed in Appendix 1: Date Imputation Rules.

Time of first onset of AE is calculated as: TEAE start date – First dose date + 1 and is categorized as:

- Week 1 ($1 \le \text{day of first onset of AE} \le 7$)
- Week 2 ($8 \le \text{day of first onset of AE} \le 14$)
- Week 3 (15 \leq day of first onset of AE \leq 21)
- Week 4 ($22 \le \text{day of first onset of AE} \le 28$)
- Weeks 5 to 8 (29 \leq day of first onset of AE \leq 56)
- Weeks 9 to 12 (57 \leq day of first onset of AE \leq 84)
- After Week 12 (84 < day of first onset of AE)

Only TEAEs are included in summary tables unless otherwise specified. If a subject has multiple episodes of events coded to the same SOC or PT, then the subject will be counted just once in the summaries for that term. Subject incidence of TEAEs by SOC and PT tables are sorted by SOCs (alphabetical order) and then by PTs (descending order) within each SOC for the overall frequency. For summaries by PT only, PTs will be sorted in descending order of overall frequency.

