Each TEAE will be summarized by treatment group.

A general overall summary of TEAEs with the number and percent of participants who experienced the following types of events will be provided:

- Participants with any TEAE
- Participants with any related TEAE
- Participants with any serious TEAE
- Participants with TEAE by severity
- Participants with an AE outcome as death
- Participants with any TEAE leading to study intervention discontinuation
- Any TEAE leading to study intervention dose reduction
- Any TEAE leading to study intervention dose interruption
- Any TEAE not recovered

Subject incidence of TEAEs tables will be summarized by the following:

- SOC and PT
- TEAE reported ≥5% in any treatment group by SOC and PT
- PT only
- TEAE reported >=5% in any treatment group by PT
- Maximum severity by SOC and PT
- Treatment-related by SOC and PT
- TEAEs of special interest by category (defined in Section 10.2.1) and PT

- TEAEs leading to permanent withdrawal of study intervention by SOC and PT
- TEAEs leading to dose reduction of study intervention by SOC and PT
- TEAEs leading to dose interruption of study intervention by SOC and PT
- TEAE by Time of First Onset, SOC, and PT
- Serious TEAE by Time of First Onset, SOC, and PT
- Serious treatment related TEAE by Time of First Onset, SOC, and PT

Separate adverse event listings will be provided including the following:

- All adverse events
- Adverse events with an outcome of death
- Adverse events leading to permanent withdrawal of study intervention
- Serious adverse events
- Adverse events of special interest, defined in defined in Section 10.2.1

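### The only time-resolved AE tables in SAP 10.2 count first onset, so events that recur or worsen at the fixed dose drop out, and the weeks when all active arms share a dose have no pooled column

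*SAP*

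**What the plan says.** **Objective.** The secondary safety objective (SAP 4.1.3) concerns the "safety and tolerability of JZP385 administered once daily for up to 12 weeks at fixed doses of 10, 20, and 30 mg/day".

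**Titration.** SAP 5.1 and Protocol 4.1 start every active arm low. For the top arm: "Participants randomized to the 30 mg/day dose will initially receive 5 mg/day from Day 1 through Day 7". After 10 mg/day on Days 8-14, that arm takes "20 mg/day from Day 15 through Day 21, and 30 mg/day starting on Day 22". The 20 mg arm reaches its dose on Day 15 and the 10 mg arm on Day 8.

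**Purpose of the 5 mg week.** Protocol 4.3 says that it is used "to evaluate whether starting at a lower dose may further improve tolerability". On timing in the phase 2a study, Protocol 4.2 reports: "Adverse events were primarily reported during the first week of treatment".

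**Counting.** SAP 10.2 tabulates TEAEs by treatment group, which for the Safety Analysis Set is the treatment actually received (SAP Section 6). The counting rule is: "If a subject has multiple episodes of events coded to the same SOC or PT, then the subject will be counted just once". The time-resolved summaries are "TEAE by Time of First Onset, SOC, and PT" and two further versions, for serious and for serious related events. The bins are Weeks 1, 2, 3, 4, 5-8, 9-12 and after Week 12. No denominator per bin is stated, and no pooled JZP385 column is named.

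**Protocol rule.** Protocol 9.4.5 says that "if a participant has multiple events with the same PT occurring in different periods, the event will be reported for each of those periods". It does not define the periods. SAP 7.6 lists three changes from the protocol, and AE counting is not among them.

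**The concern.** The AE tables are meant to describe tolerability at three fixed doses. For the first 14 days the active arms do not differ in scheduled dose, and earlier experience suggests that many events fall early. A whole-study table by arm therefore adds events from shared exposure to events at the assigned dose.

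The onset table should separate the two, but it does so only for participants who have the term for the first time. A participant with dizziness on 5 mg/day that resolves and returns at 30 mg/day appears in Week 1 and nowhere later. Protocol Appendix 4 records a rise in severity as a new AE, so a mild Week 1 event that becomes severe at the fixed dose has a new onset date that the first-onset table does not use. The participants who drop out of the later bins are those who have already shown sensitivity to the drug.

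At stake are the clarity of the safety comparison between doses, and how precisely the shared 5 mg and 10 mg weeks can be described against placebo.

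**Working it through.** **1. The plan's own figure.** Protocol 4.2 gives up to 3 weeks of titration and at least 9 weeks at the fixed dose. Days at fixed dose = 84 − (first fixed-dose day − 1):
- 10 mg: 84 − 7 = 77 days (92%)
- 20 mg: 84 − 14 = 70 days (83%)
- 30 mg: 84 − 21 = 63 days (75%), which is 9 weeks, as stated.

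**2. Scheduled dose in each SAP 10.2 onset bin (mg/day).**

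| Bin | Days | 10 mg arm | 20 mg arm | 30 mg arm |
|---|---|---|---|---|
| Week 1 | 1-7 | 5 | 5 | 5 |
| Week 2 | 8-14 | 10 | 10 | 10 |
| Week 3 | 15-21 | 10 | 20 | 20 |
| Week 4 | 22-28 | 10 | 20 | 30 |
| Weeks 5-8 | 29-56 | 10 | 20 | 30 |
| Weeks 9-12 | 57-84 | 10 | 20 | 30 |

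Each bin holds one scheduled dose per arm. First onsets are therefore attributed cleanly; later episodes are not shown.

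**3. Size of the attenuation.** The documents give no AE rates for this trial, so these inputs are assumptions. Let q be the share with the term before Day 22, f the proportion with an onset from Day 22 among those without an earlier episode, and r the same proportion among those with one.
- True late incidence = (1 − q)f + qr
- Shown in the first-onset bins = (1 − q)f
- Lost from the gap between 30 and 10 mg = q(r30 − r10)

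Under independence r = f. Take late incidence as 5% on 10 mg and 15% on 30 mg, a true gap of 10 points. Whole-study incidence is 1 − (1 − q)(1 − f).

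| q | First-onset bins, 10 / 30 mg | Gap | Whole study, 10 / 30 mg | Gap |
|---|---|---|---|---|
| 5% | 4.75% / 14.25% | 9.5 | 9.75% / 19.25% | 9.5 |
| 10% | 4.5% / 13.5% | 9.0 | 14.5% / 23.5% | 9.0 |
| 20% | 4.0% / 12.0% | 8.0 | 24.0% / 32.0% | 8.0 |
| 30% | 3.5% / 10.5% | 7.0 | 33.5% / 40.5% | 7.0 |

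The 3:1 ratio survives in the first-onset bins. In the whole-study table at q = 10% it falls to 23.5/14.5 = 1.6.

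If episodes cluster within participants and recurrence depends on dose, more is lost. With q = 10%, r = 20% on 10 mg and 60% on 30 mg (assumed), true incidence is 0.9 × 5 + 0.1 × 20 = 6.5% and 0.9 × 15 + 0.1 × 60 = 19.5%. That is a gap of 13.0 points, of which 9.0 are shown. If recurrence does not depend on dose, the gap loses nothing.

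**4. Denominator.** Protocol 9.2 assumes 20% dropout. Eight late cases (assumed) are 8.0% of 100 but 10.0% of the 80 still present. Unequal dropout between arms would distort the contrast.

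**5. Pooling in the shared weeks.** With 100 per arm (Protocol 9.2), 300 active participants share the Week 1 schedule if all are dosed. The 95% CI half-width for active minus placebo is 1.96 × √[p(1 − p)(1/n1 + 1/n2)]. At an assumed p = 10%:
- 100 v 100: 1.96 × √(0.09 × 0.02) = 8.3 points
- 300 v 100: 1.96 × √(0.09 × 0.01333) = 6.8 points

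The chance of seeing at least one case of a 1% event is 1 − 0.99^100 = 63% in one arm and 1 − 0.99^300 = 95% in three.

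**The case against.** A reader might infer that the planned tables cannot show tolerability at the fixed doses, or of the 5 mg start, at all. The documents do not support that. The bins line up with the titration steps: Week 1 shows first onsets on 5 mg against placebo, and the bins from Week 4 show new onsets at 10, 20 and 30 mg. A reader can add the three Week 1 counts by hand. This part of the defence stands.

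Other points stand in part:
- The whole-study tables include maximum severity and withdrawals, and all AEs are listed. Recurrences are therefore recorded, and the worst grade is kept, but without timing. If a recurrence is the first serious episode of a term, the serious-event onset table would presumably show it.
- Under independence the loss is modest, and the ratio between doses in the late first-onset bins is unchanged.
- The early pattern comes from studies that started at 8 mg/day (Protocol 2.2 and 4.3). A Week 1 peak at 5 mg is an extrapolation.
- The tolerability question in Protocol 4.3 is a rationale, not an objective or endpoint, and safety is descriptive (Protocol 9.1).

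A reader might also infer that the SAP plainly contradicts Protocol 9.4.5. That is unsettled. Protocol Table 3 names three periods (screening, double-blind treatment and safety follow-up), under which two episodes on treatment fall in one period. Protocol 6.3, however, speaks of a titration period. Section 9.4.5 also counts multiple increases in severity as one AE, which sits awkwardly with Appendix 4. The wording needs resolving, but it does not prove an undeclared change.

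**Conclusion.** The point holds as a gap in the summaries; it does not mean that they fail to inform. Events that recur or worsen at the fixed dose after an episode in titration are absent from the general time-resolved table, which attenuates the dose contrast. An assumed late gap of 10 points shows as 9.5, 9.0, 8.0 or 7.0 points when 5, 10, 20 or 30% had the term earlier. This rests on independence and on the same q in each arm. The second assumption is reasonable for Days 1-14, when doses are shared. It is less so for Days 15-21, when the 20 and 30 mg arms take more than the 10 mg arm; a higher q in those arms would shrink the gap further.

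Separately, no at-risk denominator is stated for the bins, and no pooled active column is planned for the shared-dose weeks. The trial has no randomised comparison of 5 mg with another starting dose, so the purpose given in Protocol 4.3 can be met only descriptively, against placebo. No hypothesis test is affected. The change is worth making because it is cheap and uses data already collected.

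**What to change.** **SAP 10.2**
1. Keep the whole-study tables by arm and the first-onset tables.
2. Add a table of TEAEs with any onset per interval: Days 1-7, 8-14, 15-21, 22-28, 29-56 and 57-84. Count a participant once per term in each interval in which an episode starts. State that a worsening recorded as a new AE counts in the interval of its own onset.
3. Use as denominator the participants who, at the start of the interval, are on treatment or within 14 days of their last dose, to match the TEAE definition. Show events after Day 84 separately, over participants in follow-up.
4. Add a pooled JZP385 column (about 300) against placebo for Days 1-7 and Days 8-14.

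A separate dose-at-onset variable is not needed, because arm and interval already give the scheduled dose.

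**Protocol 9.4.5 and SAP 7.6.** Define the periods, reconcile them with the once-only rule in SAP 10.2, and list any resulting change in SAP 7.6.

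**Protocol 4.3.** State that the trial describes tolerability of the shared starting dose against placebo and has no randomised comparison with another starting dose.

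**Cost.** SAP wording, one table and one extra column, with no new data. Interval counts will not sum to overall incidence, and an event that persists unchanged from titration still counts only where it began. Both need a footnote.

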10.2.1. Adverse Events of Special Interest

TEAEs of special interest will be summarized and may include the terms or categories noted below.

- Hallucinations of any type
- Syncope

10.3. Laboratory Assessments

The continuous clinical laboratory assessments (hematology, chemistry, and urinalysis) will be summarized at each visit using descriptive statistics. The change from Baseline will be provided at the Week 12.

Shift tables will summarize changes in clinical laboratory assessments at each of the post-baseline visit with respect to baseline. Lab values are categorized into L1, low, normal, high, or H1 based on the lab reference range. L1 and H1 values are predefined per the lab vendor alert ranges and correspond to the extreme abnormal lower and higher ranges, respectively.

Abnormal laboratory assessments deemed clinically significant by the investigator will be reported as an adverse event.

A listing of Participants with abnormal value(s) according to the following criteria will be summarized using Safety Analysis Set:

- Any laboratory value that falls into the pre-defined low or high panic ranges (L1 or H1) per the Q2 Laboratory Range Chart.
- Alanine aminotransferase (ALT) or aspartate aminotransferase (AST) \geq 3 × Upper Limit of Normal (ULN) and total bilirubin \geq 2 × ULN, inclusive (Hy's Law).
- AST or ALT \geq 5 × ULN,

- Creatinine $> 1.5 \times ULN$
- Participants positive for alcohol, urine drug screen or pregnancy assessments

All laboratory results, including pregnancy test, drug screen, and alcohol screen, will also be presented in subject data listings.

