7.2.3. Visit Windows

All scheduled, unscheduled, and early termination assessments will be summarized by derived analysis visit per the Table 5, regardless of whether the visit was performed on-site or remotely. Visit dates will be mapped based on the scheduled Period of each visit, with adjusted analysis-defined visit windows as specified in Table 5.

Table 5 Visit Windows for Assessments or Measurements

Study Period	Scheduled Visit	Scheduled Study Day	TETRAS-ADL, TETRAS-PS, CGIs	CGIc and PGIc	QUEST, SF-36v2, ETEA	C-SSRS ^b , Clinical Laboratory ^{c, e} , Urinalysis ^e , Weight, Vital Signs, Breath Alcohol ^{d, e} , ECG, Urine Pregnancy test
Screening	Visit 1/Visit 2 ^a	-49 to -8	Any Day up to -2	na	n/a	Any Day up to -2
Baseline ^f	Baseline Visit	-1	Closest prior to dosing	na	Closest prior to dosing	Closest prior to dosing
	Week 1	7 (-1, +2)	na	na	na	2 - 14
Double-Blind	Week 4	28±3	2 - 42	2 - 42	na	15 - 42
Treatment	Week 8	56± 3	43 - 70	43 - 70	na	43 - 70
	Week 12	84± 3	71 - 98	71 – 98	2 - max	71 - max
Safety Follow-up	End of Study	98± 3	na	na	2 - max	2 – max ^f

^a Screening Visit 2 is only for participants who need to wash out of any medications that impact tremor (e.g., anti-tremor medications) prior to Baseline;

^b At screening visit 1, C-SSRS screening/baseline version, at screening visit 2, C-SSRS since last visit version;

^c Clinical laboratory includes hematology and chemistry labs;

^dBreath Alcohol is not collected at W1;

^e Not collected at Safety Follow-up.

^f For participants who randomized without taking the study intervention, the Baseline Visit or latest Screening Visit (if Baseline Visit is not available) will be mapped.

If multiple assessments or measurements are recorded within a single visit window (including scheduled, unscheduled, repeated, and retest assessments or measurements as well as early discontinuation data), the following rules will be applied to determine the result from which assessment will be used for the summaries for that analysis visit.

- The priority will always be given to the scheduled visit within the corresponding visit window (e.g., scheduled W4 visit corresponds to Week 4 visit window) regardless of the relative distance to the scheduled Visit Day.
- If there are 2 or more observations within the same visit window, then the non-missing one closest to the scheduled Visit Day will be used in the analysis.

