10.4. Vital Signs

The following vital signs measurements will be reported for this study.

- Supine and standing systolic blood pressure (SBP), (millimeter of mercury [mmHg])
- Supine and standing diastolic blood pressure (DBP) (mmHg)
- Supine and standing pulse rate (beats per minutes [bpm])
- Sitting or supine respiratory rate (breaths/min)
- Body Temperature (°C)
- Weight (kg)
- Height (cm)
- BMI (kg/m2) [derived]

The orthostatic vital signs will be derived as the difference found by subtracting the supine measurement from the standing measurements. The orthostatic measurement will be summarized with the supine and standard measurements.

These vital signs (with the exception of the BMI which will be calculated programmatically) will be measured during the screening visit and each in-clinic scheduled visit. Height (cm) will be obtained at screening visit only.

The following summaries will be provided for vital signs data:

Jazz Pharmaceuticals

Statistical Analysis Plan - Protocol JZP385-201

- Observed and change from baseline by visit
- Incidence of markedly abnormal criteria by visit

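### Numeric laboratory change from baseline is planned only at Week 12, so it leaves out Weeks 1, 4 and 8 and anyone whose last sample falls before Day 71

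*SAP*

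**What the plan says.** SAP Section 10.3 plans four kinds of laboratory output.

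- Continuous hematology, chemistry and urinalysis values "will be summarized at each visit using descriptive statistics". For change, the text adds: "The change from Baseline will be provided at the Week 12". No other visit is named for it.
- Category moves are tabulated separately: "Shift tables will summarize changes in clinical laboratory assessments at each of the post-baseline visit with respect to baseline". The categories are L1, low, normal, high and H1.
- "A listing of Participants with abnormal value(s) according to the following criteria will be summarized using Safety Analysis Set". The criteria include alert-range values, Hy's Law, transaminase multiples and creatinine, and none is tied to a visit.
- "All laboratory results, including pregnancy test, drug screen, and alcohol screen, will also be presented in subject data listings".

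On early stoppers, SAP Section 7.2.3 says: "All scheduled, unscheduled, and early termination assessments will be summarized by derived analysis visit per the Table 5". The laboratory windows in Table 5 are Days 2 to 14 (Week 1), 15 to 42 (Week 4), 43 to 70 (Week 8) and 71 onward (Week 12). An empty window stays missing, and Section 7.2.5 does not impute missing safety values.

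For vital signs, SAP Section 10.4 plans "Observed and change from baseline by visit", and Section 10.5 does the same for quantitative ECG measurements. Protocol Section 9.4.5 says of laboratory data: "Observed and change from baseline laboratory evaluations will be summarized descriptively". It names no visit.

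**The concern.** The protocol's Schedule of Activities collects blood and urine at Weeks 1, 4, 8 and 12 and at early discontinuation. Three of the four scheduled on-treatment collections get no numeric change summary.

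Being absent by Week 12 is also linked to tolerability by design. Protocol Sections 4.1 and 6.5 allow no dose adjustment and take participants who cannot tolerate their assigned dose off treatment. Section 7.1 says that those who stop permanently do not remain in the study. The Week 12 change summary is therefore weighted towards participants who tolerated their dose. If intolerance differs by dose, the arms in that summary are selected differently.

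Protocol Section 4.2 notes that adverse events in the earlier essential tremor study came mainly in the first week, and it presents the repeated clinic visits as the way to assess safety over time. A change summary at the last visit only does not use that schedule. What is at stake is the description of modest or early laboratory shifts by arm, not any formal test.

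**Working it through.** **Which outputs an early stopper reaches.** Take a participant whose last sample, at the early discontinuation visit, falls on Day 50.

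| Laboratory output (SAP 10.3) | Included? | Shows own value minus own baseline, by arm? |
|---|---|---|
| Observed values by visit | Yes, in the Week 8 window | No |
| Numeric change from baseline | No, Week 12 only | Yes |
| Shift tables by visit | Yes, in the Week 8 window | Category moves only |
| Abnormal-value listing | Only if a criterion is met | No |
| Full listings | Yes | No arm summary |

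Moving that last sample to Day 75 puts it in the Week 12 window and so in the numeric change summary. What counts is the date of the sample, not whether the participant completed treatment.

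A within-person difference can be calculated at every visit. SAP Section 7.2.1 falls back on the last pre-dose value when the Baseline Visit has none, which covers participants whose baseline laboratory tests were not repeated.

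**How many could be absent.** The plan's own inflation comes first. SAP Section 5.3 gives 80 evaluable per arm and 20% dropout:

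80 / (1 − 0.20) = 100 randomised per arm, and 4 × 100 = 400 in total. This matches the plan.

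Planned dropouts are 100 × 0.20 = 20 per arm, or 80 in total. Let *f* be the share of dropouts whose last laboratory sample is before Day 71. Then

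absent per arm = 20 × *f*, and absent in total = 80 × *f*.

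The documents do not give *f*, so the values below are assumptions.

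| Assumed *f* | Per arm | Total |
|---|---|---|
| 0.50 | 10 | 40 |
| 70/84 = 0.83 (dropout uniform over 84 days) | 16.7, about 17 | 66.7, about 67 |
| 1.00 (ceiling) | 20 | 80 |

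**Comparison with the other safety data.** Protocol Section 9.4.5 asks for vital signs by scheduled visit, but names no visit for ECG intervals or for laboratory values. The SAP then gives ECG change by visit and laboratory change at Week 12 only. It states no reason for treating the two differently.

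**The case against.** The strongest reply is that the data are reported elsewhere, and much of it stands.

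- A reader might infer that Week 12 holds the only laboratory change table, or that early stoppers' results drop out of the comparison of arms. The SAP does not support this. Shift tables against baseline are planned at every post-baseline visit, and early-termination samples enter them and the observed-value summaries through the visit windows.
- A reader might infer that the Week 12 summary covers completers only. It does not, because its window runs from Day 71 onward and takes in late stoppers.
- A reader might infer that the SAP contradicts the protocol. It does not. Protocol Section 9.4.5 names no visit for laboratory change, and Section 9.4 leaves the detail to the SAP. For the same reason, the absence of this limit from SAP Section 7.6 (Changes to Planned Analyses) is not a breach.
- Marked abnormalities are well covered. Clinically significant ones become adverse events, which are tabulated by arm, by time of first onset and by whether they led to permanent withdrawal. The abnormal-value listing is independent of visit.
- Protocol Section 2.3.1 reports no clinically important laboratory trends in completed studies, and all safety analysis is descriptive.

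These points do not cover drift within the normal range. A shift table cannot show a value that moves but stays in its category. Observed means include early stoppers but do not pair each value with that person's baseline, and the participants who contribute change from visit to visit. Listings do not summarise arms.

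**Conclusion.** The point holds as a minor gap in safety reporting. SAP Section 10.3 sets a definite rule that confines the paired numeric laboratory change summary to participants with a sample on or after Day 71 and provides none at Weeks 1, 4 and 8.

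The number absent is at most about 20 per arm, and roughly 10 to 20 under the assumed timings. This rests on the planned 20% dropout applying equally to each arm and on everyone who stays having a Week 12 sample. Unequal dropout or missed samples would change the count. The documents give no dropout timing, so 20 is a ceiling and not an estimate.

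It would go too far to conclude that early stoppers' laboratory findings go unreported or that a safety signal would be hidden. The loss is limited to paired, within-range change by arm.

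**What to change.** Replace the Week 12 sentence in SAP Section 10.3 with:

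> *Change from Baseline will be provided at each scheduled post-baseline visit and at the last on-treatment value, including early-discontinuation samples.*

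The SAP should also say how long after the last dose an early-discontinuation sample still counts as on-treatment. Protocol Section 7 foresees that this visit may come two or more weeks after dosing ends.

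This brings laboratory data into line with vital signs and ECG. It uses samples already collected and windows already defined, so the cost is a few extra columns in an existing table. If Week 12 only is intended, a sentence giving the reason would be enough. Sample size, power, alpha and the efficacy analyses do not change.
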